To evaluate the impact of structured benefit-harm information in patient leaflets, we will conduct a randomized controlled trial with a nationally representative sample of adults in the United Kingdom (UK). The trial will evaluate whether including qualitative or quantitative information about drug benefits and harms improves individuals' expectations and understanding of a newly approved drug. Participants will be randomly assigned to one of three groups: (1) the standard patient information leaflet (control), (2) a leaflet incorporating the EMA's proposed key information section with qualitative statements, or (3) a leaflet with a key information section that includes both qualitative and quantitative information on the drug's benefits and harms.

Methods

This study received ethics approval from the London School of Economics and Political Science. The protocol was registered prior to recruiting participants (ClinicalTrials.gov) and the study will be reported in accordance with the CONSORT guidelines for randomized controlled trials.

Randomization

Participants will be individually randomized with equal allocation to 1 of 3 versions of a patient information leaflet: (1) the standard patient information leaflet (control), (2) a leaflet incorporating the EMA's proposed key information section with qualitative statements, or (3) a leaflet featuring a key information section that summarises quantitative data on the drug's main benefits and harms in addition to qualitative statements. We will use Qualtrics to randomize participants and to administer the survey.

Participants

Adults 18 years and older, fluent in English, and residing in the UK will be invited to participate in this survey. Participants will be recruited by Cint, a market research company that identifies participants from hundreds of research panel providers that use different methods for recruitment. We plan to recruit a nationally representative census-matched sample of adults according to age, sex, and education. Informed consent will be obtained from participants before initiating the survey; participants will be directly compensated by the survey company after completion. No identifying information about participants will be recorded.

Interventions

Participants in the control group will receive the standard patient information leaflet for a recently approved cancer drug, obtained electronically from the EMA website. There are 2 experimental conditions.

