For participants randomized to receive the EMA's proposed key information section with qualitative statements, we developed a version based on the draft proposal published by the EMA.⁹ The proposed key information section summarizes the goal of treatment, main benefits, contraindications, and most serious side effects. To ensure accuracy of our interpretation, we sought feedback from the EMA. The final version tested in the trial incorporated their suggestions.

Next, we developed a key information section that includes quantitative data on the drug's main benefits and side effects, modeled on the Drug Facts Box – a tabular summary format for prescription drugs, designed to resemble a nutrition label.¹³ The key information section presents qualitative information about the drug (including its indication and treatment goal), and how it was studied (the comparator treatment and number of patients enrolled in the clinical trial that supported the drug's approval). It supplements this with quantitative data the drug's benefits and side effects. Data on the drug's benefits and side effects were sourced from European Public Assessment Reports (EPARs). Further details are provided in the appendix.

Procedure

Upon entering the study, participants will be randomized to 1 of 3 versions of a patient leaflet. The patient leaflet is for tivozanib (Fotivda), a cancer drug approved by the EMA for the treatment of advanced kidney cancer. An electronic version of the patient leaflet along with a download link will be displayed alongside each multiple-choice question. Participants will first complete a practice question designed to test their ability to scroll through and navigate the leaflet. Participants who answer the practice question incorrectly will be excluded from the study at this stage.

The first set of questions is designed to evaluate participants' expectations, perceived magnitude, and understanding of the drug's benefits and side effects based on the information provided in the patient leaflet. To assess expectations, we will ask participants about the likelihood that patients with advanced kidney cancer would be cured, live longer, or

feel better if they were treated with tivozanib. They will also be asked about the perceived magnitude of the tivozanib's benefits and side effects.^{13–15}

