To assess understanding, we will ask participants 3 questions: (1) the approved indication of tivozanib, (2) the most common serious side effect associated with treatment, and (3) the recommended dose of treatment. Answers to all 3 questions can be found in the standard patient leaflet. Information about the drug's indication is also included in both key information sections; information about the most common serious side effect is presented in the EMA's proposed key information section with qualitative statements. Participants randomized to the key information section with both qualitative statements and quantitative data will receive 2 additional questions: one asking them to identify the difference in overall survival between tivozanib and standard treatment, and another asking about the difference in serious side effects.

Next, all participants will be asked a series of questions to assess their satisfaction with the information presented in the version of the patient leaflet they were assigned. Before ending the survey, we will ask participants for information about their demographics: their age, sex, highest level of educational attainment, and personal experience with cancer (whether themselves, an immediate family member or close friend had been diagnosed with cancer).

Primary outcome

The primary outcome of the study is participants' expectations about the drug's benefits and side effects. We selected tivozanib as the test treatment because it is representative of many recently approved cancer drugs. Tivozanib is not curative for advanced kidney cancer and, at the time of approval, it demonstrated no additional overall survival or quality of life benefit relative to standard treatment (sorafenib). Owing to the lack of information about drug benefits in the standard patient leaflet and the limited information quantifying side effects, we hypothesized that participants would overestimate the benefits and underestimate the side effects of tivozanib.¹⁴

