We assessed 3 questions related to participants' expectations about treatment outcomes: whether participants expected that tivozanib was curative, extended overall survival, or improved quality of life. We selected these 3 outcomes because research shows that patients undergoing cancer treatment value these outcomes the most.^{15,16} For the primary analysis, we will compare the proportion of participants in each group who had accurate expectations for at least 2 of the 3 treatment outcomes with tivozanib (defined as responding "definitely no" or "probably no" to these questions).

Secondary outcomes

Participants' understanding of the information presented in the patient leaflet, their perceived magnitude of the drug's benefits and harms, and their satisfaction with the information are secondary outcomes of the trial. To assess understanding, we will compare the proportion of correct responses to each comprehension question across the randomized groups. To assess participants' perceived magnitude of the drug's benefits and harms, we will compare the proportion of participants in each group who responded that (1) the benefits of tivozanib were large, (2) the side effects were not concerning, and (3) the benefits of tivozanib outweighed the side effects. To assess satisfaction, we will compare the proportion of participants in each group who provided positive ratings about the leaflet (e.g., reporting that the leaflet was helpful and easy to understand).

Quality control

We will use several strategies to enhance the reliability and validity of the survey response data. First, we have included 2 attention check questions at different points throughout the survey. The first question will validate that participants can navigate the online survey and scroll through the patient leaflet; the second question will ask participants to select a specific

answer to ensure that they are paying attention. Participants that answer either question incorrectly will be excluded from the study at that stage. We will also exclude participants that (1) do not complete the survey, (2) complete the survey but straight-line their responses, and (3) participants that complete the survey in under 180 seconds.

Statistical analysis

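### All five exclusion rules act after randomization, and no planned analysis would show whether they affect the primary comparison

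*Combined protocol and SAP*

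**What the plan says.** All references are to the combined protocol and SAP.

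- **Randomization (Procedure):** "Upon entering the study, participants will be randomized to 1 of 3 versions of a patient leaflet".
- **Practice question (Procedure; survey question 3):** participants find a word in their assigned leaflet. "Participants who answer the practice question incorrectly will be excluded from the study at this stage".
- **Both check questions (Quality control; survey questions 3 and 10):** "Participants that answer either question incorrectly will be excluded from the study at that stage".
- **Other rules (Quality control):** the plan also drops people who do not finish, and those who "complete the survey but straight-line their responses, and (3) participants that complete the survey in under 180 seconds". Straight-lining is not defined.
- **Primary outcome:** the share of each group with "accurate expectations for at least 2 of the 3 treatment outcomes with tivozanib", taken from survey questions 5 to 7. The accurate answer to each is one of the two negative options.
- **Order of the survey:** questions 5 to 7 come before the second check at question 10. Demographics come last: "Before ending the survey, we will ask participants for information about their demographics". The quantitative arm "will receive 2 additional questions" (survey questions 8 and 11), so it has 26 items against 24 in the other two arms.
- **Statistical analysis:** chi-square tests, logistic models adjusted for demographics, and subgroup analyses. The section defines no analysis population, no analysis that puts excluded people back, and no handling of missing primary answers.
- **Reporting (Methods):** "the study will be reported in accordance with the CONSORT guidelines for randomized controlled trials".

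**The concern.** Randomization makes the three groups comparable at entry. Each of the five rules then selects people after that point. Apart from non-completion at survey questions 1 and 2, which precede the leaflet, each also acts after the assigned leaflet has been shown.

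The analysed groups can come to differ in more than the leaflet in two ways. The share excluded may differ by arm while the excluded differ in accuracy from the rest. Or the shares may be equal while different kinds of people are removed in each arm. In either case the planned analyses cannot separate a leaflet effect, or its absence, from the filter. Adjusting for demographics does not help, because people who leave before the last section have none recorded.

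**Working it through.** **The plan's own figure.** Inputs from Statistical analysis: 60% vs 50%, 90% power, two-sided 0.05 over three comparisons, so 0.05/3 = 0.0167.

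n = [2.394·√(2·0.55·0.45) + 1.282·√(0.6·0.4 + 0.5·0.5)]² / 0.10² = 667 per group, or 687 with continuity correction. The plan's 700 is consistent with this, and power at 700 is 91.5%.

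**Bias from the filter.** The documents give no exclusion rates and no accuracy for the excluded, so the following are assumptions: no true effect, 50% accurate among all randomized in every arm, and 700 randomized per arm. Let e be the share excluded in an arm and a the accuracy of those excluded.

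Analysed proportion = (0.5 − e·a)/(1 − e)

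False positives come from a two-sided pooled z test at 0.05/3 with 700·(1 − e) per arm.

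| Excluded (arm 1 vs arm 2) | Accuracy of excluded | Analysed proportions | Spurious difference | False positives |
|---|---|---|---|---|
| 12% vs 10% | 30% in both | 52.7% vs 52.2% | +0.5 points | 1.8% |
| 15% vs 10% | 30% in both | 53.5% vs 52.2% | +1.3 | 2.9% |
| 20% vs 10% | 30% in both | 55.0% vs 52.2% | +2.8 | 7.6% |
| 20% vs 10% | 70% in both | 45.0% vs 47.8% | −2.8 | 7.6% |
| 20% vs 10% | 50% in both | 50.0% vs 50.0% | 0 | 1.67% |
| 10% vs 10% | 30% vs 50% | 52.2% vs 50.0% | +2.2 | 5.5% |
| 20% vs 20% | 30% vs 50% | 55.0% vs 50.0% | +5.0 | 23.6% |

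Worked example, sixth row: (0.5 − 0.10·0.3)/0.90 = 0.522 and (0.5 − 0.10·0.5)/0.90 = 0.500. Swapping the arms reverses the sign. The last two rows have identical exclusion counts and still show bias.

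**Random clicking.** Two of the four options are accurate on each primary item, so a random clicker gets at least 2 of 3 right with probability 3/8 + 1/8 = 50%. Removing only such people, at any rates, leaves the assumed 50% unchanged.

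**What can be recovered.** People removed at question 10, for speed or for straight-lining, and people who leave after question 7, have already answered questions 5 to 7. People removed at question 3 have not. For missing answers, the best-case and worst-case bounds are together as wide as the two missing shares added:

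- 20% vs 10% missing, with the missing 30% accurate: observed accurate shares of those randomized are 0.44 and 0.47. The bounds run from 0.44 − 0.57 = −13 points to 0.64 − 0.47 = +17 points.
- 3% vs 2% missing, same accuracy: −2.3 to +2.7 points.

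**Separate point, power.** If 700 is counted before exclusions, a 10% loss leaves 630 per group (88.1% power) and a 20% loss leaves 560 (83.5%). Since 667 are needed for 90%, any loss above 33/700 = 4.7% falls short.

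**The case against.** The filter is prespecified, has a clear purpose, and removes answers that may carry little information. If it removes only random clickers, the figures above show no bias at a 50% rate. CONSORT reporting should disclose how many people were removed in each arm.

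These points support keeping the filtered analysis. They do not supply the missing check. Prespecification does not restore comparability lost after randomization, people who speed or leave need not answer at random, and counts by arm do not show how accurate the removed people were.

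A reader might go further and infer that the rules do act differently by arm, or that they favour a particular arm. The documents do not support that:

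- **Practice question.** It is answered in an arm-specific leaflet, but section 3 is base-leaflet text with the same answer in every arm.
- **180-second limit.** It covers two more items in the quantitative arm, and reading time may differ, but nothing shows that it removes different shares.
- **Straight-lining.** A rule that counted questions 5 to 7 could remove accurate responders, since every accurate answer there is negative. Those questions sit on separate pages, however, and the phrase reads more naturally as applying across the survey. In the printed order, the correct options for questions 3 and 10 are in different positions, so someone choosing one position throughout would already fail a check. What stands is that the rule is undefined.

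The opposite inference, that similar exclusion counts would settle the matter, also fails. It assumes the excluded are equally accurate in every arm.

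**Conclusion.** The point holds as a gap in the analysis plan. Five rules select participants after randomization, and no planned analysis would reveal an effect on the primary comparison. It is not a finding that the result will be biased: size and direction are unknown. Under the stated assumptions the spurious difference ranges from zero to 5.0 points in either direction, against a design difference of 10 points. False positives range from the nominal 1.67% to 23.6%. These figures rest on assumed exclusion shares and accuracies, not on anything the documents report.

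The document facts are certain; the consequence is only possible. Because the remedy is inexpensive, it should be made. The filtered comparison can remain primary. Whether 700 per group is counted before or after exclusions is a separate ambiguity and has no bearing on bias.

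**What to change.** 1. Put the navigation practice question before randomization, using base-leaflet text common to all arms.
2. Record a failure at question 10 as a flag instead of ending the survey. Where the consent terms allow, keep the answers to questions 5 to 7 from people who fail that check, speed, straight-line or leave after question 7.
3. Keep the filtered analysis as primary. Prespecify one sensitivity analysis, by assigned arm, of everyone randomized who answered questions 5 to 7, with best-case and worst-case bounds for missing answers. Use the unadjusted chi-square test, because early leavers have no covariates. State in advance that the primary result will be called robust only if the two analyses agree.
4. Define straight-lining in advance on items other than questions 5 to 7, and report exclusions by arm and reason.
5. Separately, state that 700 per group is the analysed number, or restate the power for the expected loss.

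**Cost.** A small change to the survey flow, possibly some extra panel payments because compensation follows completion, and one added analysis. That analysis is diluted by inattentive respondents. If 10% in each arm are inattentive and 30%, 50% or 70% of them are accurate, the contrast becomes 57% vs 48%, 59% vs 50% or 61% vs 52%. Power at 700 per group is then 83.7%, 83.9% or 84.3%, against 88.1% if they are dropped. This is why the filtered analysis stays primary. The added analysis still conditions on having answered questions 5 to 7, and the bounds inform only if few of those answers are missing, which is the aim of steps 1 and 2.

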The sample size and power calculations for this trial were informed by previous studies.¹³ This trial is powered to detect an absolute difference of 10% between groups (60% vs 50%) with 90% power and a two-sided alpha of 0.05. We plan to adjust for 3 pairwise comparisons for the primary outcome, comparing each of the intervention arms with one another. Therefore, we aimed to recruit 700 participants per group and considered Bonferroni-corrected p values <0.0167 to be statistically significant.

We will use χ^2 tests to compare the difference in proportions between groups. Logistic regression models will be used for adjusted analyses, controlling for participant demographics. We will conduct additional subgroup analyses to explore heterogeneity of treatment effects based on participants' sex, age, education level, and personal experience with cancer.

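### Optional improvement, not an error: with three groups, a pre-specified Shaffer step-down rule finds true differences more often than a flat 0.0167 for every contrast, with no extra participants

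*Combined protocol and SAP*

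**What the plan says.** The Statistical analysis section gives the design target: "This trial is powered to detect an absolute difference of 10% between groups (60% vs 50%) with 90% power", at an overall two-sided alpha of 0.05. On multiplicity it says: "We plan to adjust for 3 pairwise comparisons for the primary outcome, comparing each of the intervention arms with one another". It continues: "Therefore, we aimed to recruit 700 participants per group", and the investigators "considered Bonferroni-corrected p values <0.0167 to be statistically significant". The tests are chi-square tests of proportions. No step-down or closed procedure is mentioned, and no confidence intervals are specified.

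The Quality control section removes people after randomisation: "Participants that answer either question incorrectly will be excluded from the study at that stage", and "We will also exclude participants that (1) do not complete the survey". It also removes straight-liners and anyone who finishes in under 180 seconds. No exclusion rate is given, and the plan does not say whether 700 is counted before or after these exclusions.

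**The concern.** All three contrasts are confirmatory: each key information section against the standard leaflet, and the two sections against each other. Under the flat rule, the second and third contrasts stay at 0.0167 even when a first difference has already been shown. With exactly three groups that strictness is not needed to control the familywise error. If groups A and B differ, then A = C and B = C cannot both hold, so at most one true null remains and there is nothing further to divide alpha between. What is at stake is some power on the remaining contrasts, not validity.

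The wording also has a small ambiguity. A Bonferroni-corrected p value is compared with 0.05, whereas 0.0167 is the threshold for an unadjusted one. Read literally, the sentence corrects twice.

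**Working it through.** **Inputs from the Statistical analysis and Randomization sections:** rates 60% vs 50%, power 90%, two-sided alpha 0.05, three pairwise contrasts, equal allocation, 700 per group. **Assumption:** the third group's rate, which the plan does not give; three patterns are shown.

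**Step 1: reproduce the plan's figure.** Pooled two-proportion formula:

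n = [z(1−α/2)·√(2·p̄·(1−p̄)) + z(0.90)·√(p₁(1−p₁) + p₂(1−p₂))]² / d²

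Here p̄ = 0.55, so √(2 × 0.55 × 0.45) = 0.7036. Also √(0.25 + 0.24) = 0.7000, d = 0.10 and z(0.90) = 1.2816.

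- α = 0.05/3 (z = 2.394): (1.6843 + 0.8971)² / 0.01 = 666.4, so 667 per group.
- α = 0.05 (z = 1.960): (1.3790 + 0.8971)² / 0.01 = 518.0, so 519 per group.
- α = 0.05/9 (the literal double correction): 812 per group.

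Power at n = 700 and α = 0.05/3 is Φ[(0.10 × √700 − 1.6843) / 0.7000] = Φ(1.373) = 91.5%. So 700 already reflects one Bonferroni correction, and the double correction was not intended.

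**Step 2: the two rules.**

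- Flat: reject each contrast with p < 0.05/3.
- Step-down: if the smallest p is < 0.05/3, reject that contrast and test the other two at 0.05 each; otherwise reject none.

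The first hurdle is the same, so every flat rejection is kept.

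**Step 3: compare them.** The figures come from exact enumeration of three independent binomials, using pooled chi-square tests without continuity correction. A separate simulation of 1,000,000 trials per scenario agrees to within about 0.1 percentage point.

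| True rates (%) | Analysed per group | Quantity | Flat | Step-down |
|---|---|---|---|---|
| 50/50/60 | 700 | Power per true contrast | 91.6% | 95.3% |
| 50/50/60 | 700 | Both true contrasts found | 85.6% | 93.0% |
| 50/50/60 | 700 | At least one true contrast found | 97.5% | 97.5% |
| 50/50/60 | 700 | False rejection of the one true null | 1.7% | 5.1% |
| 50/60/60 | 700 | Power per true contrast | 91.6% | 95.2% |
| 50/55/60 | 700 | 10-point contrast | 91.6% | 92.2% |
| 50/55/60 | 700 | Each 5-point contrast | about 30.5% | about 46.2% |
| 50/50/50 | 700 | Familywise error | 4.6% | 4.6% |
| 50/50/60 | 665 | Power per true contrast | 89.9% | about 94% |
| 50/50/60 | 600 | Power per true contrast | 86.0% | 91.5% |
| 50/55/60 | 600 | 10-point contrast | 86.0% | 87.0% |

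The 5.1% is the actual size of a single uncorrected chi-square test at nominal 0.05; with continuity correction it is 4.5%. No flat rejection was lost in any scenario.

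**Step 4: agreement with intervals.** A 98.3% unpooled Wald interval would include zero for at least one contrast called significant by the step-down rule in 1.3% of trials with all groups equal, 10.2% at 50/50/60 and 29.1% at 50/55/60.

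**The case against.** The plan sets one power target and meets it with 700 analysed per group, so choosing another valid multiplicity rule is a matter of preference. That stands, and it is why this is an optional change.

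The gain depends on the pattern. The arms are graded in content, so an intermediate middle group is plausible. In that case the one contrast the trial is sized for gains 0.6 points, while the 5-point contrasts improve but stay below 50% power. That stands too.

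The extra false positives fall on a contrast that matters. If both key information sections work equally well, the step-down rule claims a difference between them about three times as often as the flat rule. That rate is still only the nominal 5% that the plan accepts for the family.

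Shaffer's rule is not the only candidate. A 2-df chi-square gate followed by pairwise tests at 0.05 is also a closed test for three groups. In simulation at 50/50/60 it did slightly better: 95.8% against 95.3% per true contrast, and 98.0% against 97.5% for at least one. Its familywise error was 5.0% with all groups at 50%. This does not make Shaffer's rule unsound. Shaffer's rule has the practical advantage of keeping the plan's three tests and its first threshold.

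Finally, the section mixes past and future tense, so the documents do not settle whether outcome data had been seen. If they had, the change is no longer available.

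**Conclusion.** The concern holds as an inexpensive improvement. The flat rule controls the familywise error and is adequately powered at 700 analysed per group. The step-down rule never loses a flat rejection and keeps nominal familywise error at 5%. It adds about 3.7 points of power per true contrast when two groups share a rate (95.3 − 91.6), and 0.6 points for the 10-point contrast when the middle group lies halfway. It does not raise the chance of finding at least one difference, and finding both true contrasts is not a target the plan set.

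These sizes rest on assumed third-group rates and on 700 analysed per group. The rule does not replace an allowance for exclusions: at 50/55/60 with 600 analysed, the 10-point contrast reaches only 87.0%. Keeping flat Bonferroni for its single threshold and closely matching 98.3% intervals is a legitimate choice.

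**What to change.** If no outcome data have been seen, make a dated amendment that replaces the significance sentence with: *Unadjusted chi-square p values for the three contrasts will be ordered. If the smallest is below 0.05/3 (0.0167), that comparison is significant and the other two are each tested at 0.05; otherwise none is significant.* Equivalently, report for each contrast the adjusted p = min(1, max(3 × smallest p, own p)) and compare it with 0.05.

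In the same amendment, say whether 700 per group means participants analysed after the Quality control exclusions, or give the expected analysed number. If intervals will be reported, state that the step-down rule, not the interval, decides significance.

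If outcome data have been seen, or the flat rule is kept, change only the wording so that 0.0167 is the threshold for unadjusted p values.

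The cost is one sentence and a dated amendment, with no added participants. The date matters because the protocol was registered before recruitment, and a later move to a more permissive rule would look opportunistic. The statistical costs are the rise from 1.7% to 5.1% in false rejection of a lone true null, and the loss of a simple interval that matches the decisions.

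### The primary chi-square test is valid and adequately powered but leaves collected demographics unused, and the adjusted logistic analysis names no effect measure; a standardised risk difference would address both, for a modest gain

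*Combined protocol and SAP*

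**What the plan says.** Under Primary outcome, the primary analysis compares, between groups, the proportion of participants with accurate expectations on at least two of three treatment outcomes. Under Statistical analysis, the design target is 60% against 50%, "with 90% power and a two-sided alpha of 0.05". The same paragraph adds "We plan to adjust for 3 pairwise comparisons for the primary outcome", and the authors "considered Bonferroni-corrected p values <0.0167 to be statistically significant". On size, "we aimed to recruit 700 participants per group".

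Proportions are compared with chi-square tests. Covariates are covered by one sentence: "Logistic regression models will be used for adjusted analyses, controlling for participant demographics". Subgroup analyses by sex, age, education and cancer experience follow. Nothing states the effect measure of the logistic model, its covariates and their coding, or any step that turns it into a risk difference.

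Under Procedure, before the survey ends, "we will ask participants for information about their demographics". The items listed there are age, sex, education and personal experience with cancer. The questionnaire's demographics section also asks yearly income, so the term demographics has two possible readings. Under Quality control, people who do not complete the survey are excluded, so everyone analysed should have reached these items.

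**The concern.** Two features deserve attention.

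**Unused information.** The primary test uses only arm and outcome. If age, education or cancer experience predict accurate expectations, as is plausible for a comprehension task, an adjusted estimate of the same difference would have a smaller standard error at no cost in data collection.

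**Scale.** The design quantity is a marginal difference in proportions. Fitted without a further step, a logistic model yields a conditional odds ratio. Odds ratios are non-collapsible: with perfectly balanced arms, the conditional odds ratio still lies further from 1 than the marginal one when covariates are prognostic. With event rates of 50% to 60% it is also well above the risk ratio. A reader who sees the unadjusted and adjusted results side by side could take the shift for confounding, or take the odds ratio for a larger effect.

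At stake are a little precision and the clarity with which the adjusted result can be set against the 10-point target.

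**Working it through.** **Inputs from Statistical analysis:** p1 = 0.60, p0 = 0.50, 700 per group, three comparisons, alpha per comparison 0.05/3 = 0.0167 two-sided (z = 2.394), power 90% (z = 1.282). **Assumed:** R², the share of outcome variance explained by the demographics. The documents give no figure; 0.01 to 0.10 is used.

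**1. Reproduce the plan's sample size.** With mean proportion 0.55,

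n = [2.394 × √(2 × 0.55 × 0.45) + 1.282 × √(0.24 + 0.25)]² / 0.10² = (1.684 + 0.897)² / 0.01 ≈ 667 per group,

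or 687 with continuity correction. At an uncorrected alpha of 0.05 the figure would be 519, so 700 already allows for the Bonferroni correction. Power at 700 is Φ[(0.10 × √700 − 1.684) / √0.49] = 91.5%. The plan's figure is supported.

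**2. Gain from adjustment.** The variance of the risk difference is multiplied by (1 − R²), so the effective n is 700/(1 − R²). The unadjusted standard error is √(0.49/700) = 2.65 points, and the 98.33% half-width is 2.394 × 2.65 = 6.33 points.

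| R² (assumed) | Effective n | Power | Reduction in SE | 98.33% half-width (points) |
|---|---|---|---|---|
| 0 | 700 | 91.5% | 0 | 6.33 |
| 0.01 | 707 | 91.8% | 0.5% | 6.30 |
| 0.05 | 737 | 92.9% | 2.5% | 6.17 |
| 0.10 | 778 | 94.3% | 5.1% | 6.01 |

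The gain in power is 0.3 to 2.8 points.

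**3. Simulation check** (2,000 trials per scenario, 700 per arm, invented covariate effects). At R² of 0.08, power was 91.0% for chi-square, 92.9% for the logistic Wald test and 93.2% for the standardised risk difference. Nearly all the gain therefore comes from adjusting; what standardisation adds is the scale. Across scenarios the standardised risk difference averaged 9.8 to 10.1 points, so the estimand is preserved.

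**4. Scale.** 60% against 50% is a risk difference of 10 points, a risk ratio of 0.60/0.50 = 1.20 and an odds ratio of (0.6/0.4)/(0.5/0.5) = 1.50. Take a balanced binary covariate with log-odds effect ±b, hold the marginal rates at 50% and 60%, and solve for the arm intercepts:

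| b (assumed) | R² implied | Conditional odds ratio |
|---|---|---|
| 0.20 | 0.01 | 1.51 |
| 0.50 | 0.06 | 1.54 |
| 0.66 | 0.10 | 1.57 |
| 1.00 | 0.21 | 1.67 |

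Over the R² range used for power, the shift is from 1.50 to between 1.51 and 1.57. Separately, an odds ratio of 1.50 does not map to one absolute difference: it means 10.0 points at a base rate of 40% or 50%, 9.1 at 30% and 7.3 at 20%.

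**The case against.** The strongest reply is that an unadjusted test is a sound choice here. Allocation is individual and equal with no stratification described, so no design factor has to enter the model. The test needs no modelling decisions and exceeds its power target. The primary result is already on the scale of the design target, and only a supportive analysis might be on another. All of this stands.

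A reader might infer more than the documents support:

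- **That the adjusted result will be reported as an odds ratio.** The plan never says so. The effect measure is unstated, and an odds ratio is only the usual default.
- **That the adjusted result cannot be set against 10 points.** The same fitted model, standardised, gives an adjusted risk difference, and nothing in the plan rules that out.
- **That the trial is underpowered or its primary test wrong.** Neither follows: 667 to 687 per group are needed and 700 are planned.
- **That the odds ratio would shift greatly.** A conditional value of 1.67 needs covariates explaining about 21% of outcome variance, twice the top of the assumed range.

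It can also be said that adjustment brings coding choices into the confirmatory test: the select-all cancer item, the Other category for sex, and whether income is included. That is true, but these can be settled in a short pre-specified statement.

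Finally, the demographics are asked after the leaflet has been seen. Age, sex, education and cancer history are unlikely to be changed by it, so this is a caveat and does not bar adjustment.

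**Conclusion.** The point holds as a modest improvement in efficiency and clarity. The chi-square comparison is valid and gives 91.5% power with 700 analysed per group, but it leaves available prognostic information unused. The adjusted analysis is silent on its effect measure, and its default output does not compare directly with the 10-point difference.

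The expected benefit is 0.3 to 2.8 points of power, or a standard error 0.5% to 5% smaller, for R² of 0.01 to 0.10. That range is an assumption; if the demographics barely predict the outcome, the gain is negligible. The scale argument has a similar size: about 1.51 to 1.57 conditionally against 1.50 marginally.

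The 91.5% assumes that 700 is the number analysed. The plan excludes participants after randomisation and gives no expected rate. If 700 were the number randomised, 90% power would hold only while exclusions stayed below about 4.7% (1 − 667/700), so a small gain in precision would be useful.

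**What to change.** Before outcome data are seen, amend Statistical analysis as follows:

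- **Primary estimate.** For each pairwise comparison, fit a logistic model with arm, age group, sex, education and cancer experience. Standardise over the analysed sample to obtain the marginal risk difference, with a robust or delta-method standard error and a 98.33% confidence interval, tested at 0.0167.
- **Sensitivity analysis.** Keep the unadjusted chi-square test and the raw difference in proportions.
- **Covariates.** State the coding of the select-all cancer item and of the Other category for sex, and whether income is included. State also whether each comparison uses a two-arm model or one three-arm model.

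If the sponsor prefers to keep chi-square as primary, the minimum is to name the covariates and report the adjusted result as a risk difference.

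The cost is a few sentences in the plan, a few lines of code, and slightly more complex analysis and reporting. The report should also note that the covariates were collected after leaflet exposure. No new data or change in sample size is needed.
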